1.5 SAMPLE SIZE

A sample size of 32 subjects was selected based primarily on practical considerations. A sample size of 32 will yield 8 complete replications of each sequence for the experiment, assuming there is no dropout or other loss of response data. No imputations are planned for lost data; however, subjects who dropout may be replaced at the discretion of the sponsor.

1.6 RANDOMIZATION

Each subject will be assigned to one of 4 test product sequences using a Williams design. The Williams design employs a Latin square, in which no test-product follows another specific test-product more than once in a given replication of the experiment (e.g., B will never follow A more than once in a 4x4 crossover design matrix). This property yields a balanced cross-over design wherein there is uniformity within both periods and sequences. In a balanced design, each of the test product types occurs the same number of times in each period and the number of subjects who receive test product type i in one period and test product type j in the next period is the same for all $i \neq j$ (Jones and Kenward 2003).

For this study, if the 4 test products are designated A, B, C, and D, the following 4x4 matrix (Table 2) represents one possible assignment of the 4 possible sequences to 4 different subjects. Thus the matrix represents one complete replication of the 4-period-4-sequence crossover experiment.

Table 2. Test Product Type Assignment in a Single Replication of a 4x4 Williams Crossover Design

Sequence	Test product type Assignment By Period			
	1	2	3	4
1	A	B	D	C
2	B	C	A	D
3	C	D	B	A
4	D	A	C	B

The randomizations will be done using a SAS macro program.^[6]

1.7 STUDY PROCEDURES

At Visit 1 (screening), subjects (21–65 years of age) will complete vital sign assessment, serum pregnancy test (female subjects), urine drug/alcohol screen, the Demographics Questionnaire and Tobacco and Nicotine Product-Use History Questionnaire, blood hematology, clinical chemistry, urinalysis, 12 lead ECG and a physical exam.

Approximately 32 eligible adult subjects (no more than 60% of either sex) may enroll into the study. Subjects will self-report that they have been using EVPs “some days” or “every day” for the past 30 days and for at least 4 out of the past 7 days.

At Visit 2, upon arrival at the site, vital signs, urine pregnancy test (female subjects), and urine drug/alcohol screen will be conducted. After check in, subjects will engage in a brief product trial with each e vapor product following an assigned schedule (i.e., ad libitum use for 10 minutes) to get accustomed to using the products. Trials of each e-vapor product will be separated by approximately 30 minutes (from the end of each product trial). Subjects who react negatively (i.e., unwilling to use and/or cannot tolerate the product [e.g., experience adverse events (AEs) that will prevent them from continuing to use the product as judged by the investigator]) to any of the Nu Mark e-vapor products during the product trial will not continue in the study. Subjects will be given a facilitated “Use the Product Again Questionnaire” after the product trials. After all assessments are complete on Day –1, subjects will be randomly assigned to a test product use schedule (1 Test Product per day for four days). Subjects will abstain from tobacco or nicotine use overnight. On Day 1, Subjects will complete an

Statistical Analysis Plan

exhaled breath test product use session with their assigned test product. An exhaled breath test product use session will consist of the following: one sample with an empty cartridge and inactive battery [sham condition] and one sample using the assigned test product with all exhaled breath collected in one type of trapping container, followed by at least 45 minutes of rest, then the sham sample and same test product sample collection with a second type of trapping container. Each sample will consist of all the exhaled breath occurring during 10 puffs, each with 5 second puff duration (+/- 1 second), over approximately 5 minutes (one puff approximately every 30 seconds) collected in the respective sample collection container:

- Trapping Container 1: captures nicotine, glycerin, propylene glycol, and menthol
- Trapping Container 2: captures formaldehyde, acetaldehyde, and acrolein
- Test product cartridges will be weighed before and after each collection.

Upon completion of the exhaled breath product use session, the subjects will be allowed to use new cartridges with freshly charged “BVR2.3 Rev 05 batteries with topography v1” batteries ad libitum for the next 12 hours following the package insert instructions. These batteries have been verified to perform within acceptance criteria of batteries without topography chip. Cartridges will be weighed before and after use. The “BVR2.3 Rev 05 battery with topography v1” will record all puffs and duration of puff during the 12 hours of ad libitum use. After the 12 hours of ad libitum use, subjects will complete the Use the Product Again Questionnaire.

After overnight tobacco and nicotine abstinence, the subjects will have vital signs recorded and repeat the exhaled breath test product use session and 12-hour ad libitum use session with their assigned test product on days 2 through 4 (1 test product per day). After each 12-hour ad libitum use session, subjects will complete the Use the Product Again Questionnaire.

Upon completion of the ad libitum product use session on Day 4, subjects will undergo end-of-study assessments and be released from the site.

The 4 test products are described in Section 1.3. The Schedule of Assessments (SOA) is provided in Table 3.

Statistical Analysis Plan

Table 3. Schedule of Assessments

EVENT	Visit 1 (Day -30 to Day -1)	Visit 2 (Day -1 Check-in)	Visit 2 (Day 1 through Day	End of Study
Age verification	X			
Informed consent	X			
Medical history	X			
Review of inclusion and exclusion criteria	X	X		
Demographics (including questionnaire)	X			
Tobacco and Nicotine Product-Use History Questionnaire				
Vital signs ¹	X	X	X	
Urine cotinine measurement	X			
HIV, HBsAg, anti-HCV screening	X			
Body weight, body height, and body mass index	X			
Clinical chemistry, hematology, and urinalysis	X			
Urine drug and alcohol screening ²	X	X		
Serum pregnancy test (all females only)	X			
Urine pregnancy test (all females only)		X		
FSH test (post-menopausal females only)	X			
Review of concomitant medications	X	X	X	X
Quit Assist™ Website Referral	X			X
Review of adverse events	X	X	X	X
Electrocardiogram	X			
Physical examination	X			X ³
Check-in procedures		X		
Confinement		X	X	
Product trial		X		
Willing To Use Questionnaire		X		
Weigh cartridges before and after use (both exhaled breath product use session and ad libitum use session) record batteries used with each cartridge			X	
Exhaled breath product use session ⁴			X	
12 hour ad libitum use with “BVR2.3 Rev 05 battery with topography v2” for recording puff parameters. The batteries used with each cartridge will be documented.			X	
Use the Product Again Question (after each 12 hour ad libitum use session)			X	
Discharge from clinic				X

HIV = human immunodeficiency virus; HBsAg = hepatitis B surface antigen; HCV = hepatitis C virus.

1. Vital signs (respiratory rate, pulse rate, blood pressure, oral temperature), will be measured in the sitting position after at least 5 minutes of rest at least 15 minutes from last tobacco use.
2. Exhaled breath test for alcohol is also acceptable.
3. Brief physical examination (symptom driven).
4. A product use session will consist of the following: one sample with an empty cartridge and inactive battery [sham condition] and one sample using the assigned test product with all exhaled breath collected in one type of trapping container, followed by at least 45 minutes of rest, then the sham sample and same test product sample collection with a second type of trapping container. Each sample will consist of all the exhaled breath occurring during 10 puffs, each with 5 second puff duration (+/- 1 second), over approximately 5 minutes (one puff approximately every 30 seconds) collected in the respective sample collection containers

Statistical Analysis Plan

2.0 STUDY POPULATIONS**2.1 DEFINITIONS OF POPULATIONS FOR ANALYSIS****2.1.1 Exhaled Breath Population**

The Exhaled Breath Population (referred in the Protocol as “the Exhaled Breath Population”) will include all subjects who used at least one test product and from whom at least 1 exhaled breath was collected.

2.1.2 Per-Protocol Population

The per-protocol (PP) population will include all subjects who sufficiently comply with the protocol and who do not have any major protocol deviations (Section 2.3).

2.1.3 Safety Population

The safety analysis set will include all subjects who used at least 1 of the study products.

2.1 PROTOCOL DEVIATIONS

Major protocol deviations will include non-compliance with inclusion criteria 3, 4 or 5 and/or exclusion criteria 7, 11, 19, and 20. (All inclusion and exclusion criteria can be seen in Sections 4.1 and 4.2 of the protocol.) major protocol deviation designations will be reviewed and updated (as necessary) shortly after the completion of the study. Decisions as to what to do about subjects who had major protocol deviations will be made at that time.

All protocol deviations will be documented and included in an appendix listing.

Statistical Analysis Plan

3.0 ENDPOINTS AND COVARIATES

3.1 PRIMARY ENDPOINT

The primary endpoints for the study are each subject's sham-corrected amount of nicotine, glycerin, propylene glycol, menthol, formaldehyde, acetaldehyde and acrolein in exhaled breath from 10 puffs in each period for each of the 4 e-vapor products.

3.2 SECONDARY ENDPOINTS

Secondary endpoints will include:

Cartridge weight changes (before and after exhaled breath sessions), cartridge weight changes per cartridge and in total during 12 hours of ad libitum use, puff count, and average puff duration per cartridge and in total by subject during 12 hours of ad libitum use, and responses to Use Product Again Questionnaire.

3.3 SAFETY ENDPOINTS

The safety endpoints of the study are:

- Vital signs (pulse rate, diastolic and systolic blood pressure)
- Adverse events

Statistical Analysis Plan

4.0 STATISTICAL ANALYSIS SPECIFICATIONS**4.1 GENERAL**

Unless otherwise stated, all data will be listed by subject, study product, and study day (and time point as necessary) and summarized by test product and study day (and time point as necessary). Tabular summaries (by test product and visit) of continuous endpoints will include standard descriptive statistics (number of observations, mean, median, SD, CV%, and range). Categorical data will be summarized as counts and percentages of numbers of subjects in each category (e.g., male and female genders). For categorical measurements (e.g., adverse experience severity) collected at separate visits, the denominator of the percentages of each category will be the number of subjects with a nonmissing value at the visit. For all other categorical measurements, except where otherwise noted, the denominator of percentages will be the number of subjects with nonmissing response data for the test product group.

For all analyses, the baseline response and covariate values will be defined per Section 1.4 of this statistical analysis plan. The electronic case report forms will be used to capture study results and data.

All tables and listings will be produced by using SAS®, Version 9.4.

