4.5 Discontinuation Procedures

Subjects who are initially confirmed as eligible during screening but are deemed ineligible before enrollment (randomization) will be considered a “screen failure.”

If premature withdrawal from the study occurs for any reason, the investigator must determine the primary reason and record this information in the case report form (CRF). Subjects withdrawn or dismissed by the investigator after enrollment (Day 1) will undergo End of Study procedures as feasible.

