4. Cartridge (only test product cartridges) will be weighed within 90 minutes prior to the first 10 puffs. The cartridge will be weighed again after the first exhaled breath measurement and before the second exhaled breath measurement.
5. 10 sham puffs (empty cartridge and inactive battery)
 - 5-second puff duration, one puff every 30 seconds (Note: All exhaled breath will be captured after the first puff to ~60 seconds after the last puff in Trapping Container 2 with a nose clip in place.) All puff durations will be documented.
 - Subjects will be instructed to inhale as they normally use EVPs and not to only mouth puff.
 - Subjects will also be instructed to make every attempt to exhale directly into the collection device and minimize leakage of the exhaled vapor in the ambient air.
6. 10 puffs with the test product
 - 5-second puff duration, one puff every 30 seconds (Note: All exhaled breath will be captured after the first puff to ~60 seconds after the last puff in Trapping Container 2 with a nose clip in place.) All puff durations will be documented.
 - Subjects will be instructed to inhale the vapor as they normally use EVPs and not to only mouth puff.
 - Subjects will also be instructed to make every attempt to exhale directly into the collection device and minimize leakage of the exhaled vapor in the ambient air.
 - Weigh cartridge (test product only) again (within 90 minutes)
- Subject will be allowed to use new cartridges with fully charged (within 24hrs) “BVR2.3 Rev 05 batteries with topography v2” batteries ad libitum for the next 12 hours
- Measure weight of cartridges before and after ad libitum use (within 90 minutes)
- Record all cartridges used with each “BVR2.3 Rev 05 battery with topography v2”. All start and stop times with each cartridge and “BVR2.3 Rev 05 battery with topography v2” will be documented.
- Document likelihood of subject using product again (Use the Product Again Questionnaire) after each 12-hour ad libitum use session
- Review concomitant medications and AEs

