6.4 USE TEST-PRODUCTS AGAIN SCORES

“Use the Product Again” VAS raw scores which can range from 0 to 100 mm (measured from left to right on the VAS), will be included in subject listings, but no summary statistics will be computed from them. The raw scores will be converted to a binary, “unwilling” vs. “willing” to use, response as follows:

VAS < 50 mm ≈ unwilling to use again VAS \geq 50 mm ≈ willing to use again.

Statistical Analysis Plan

An additional 3-level ordinal response will be defined as follows:

VAS < 50 mm ≈ unwilling to use again VAS = 50 mm ≈ don't care

VAS > 50 mm ≈ willing to use again.

Summary statistics [n (%)] will be computed for each level of the binary and 3-level endpoint, by test-product and by sequence. Summary statistics (n, minimum, maximum, median, mean, and standard deviation) of raw VAS scores will be computed by test-product, sequence and by binary “willing to use” category.

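### A subject who withdraws because of a product before that day's willingness question drops out of that product's percentage, which would then be biased upward

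*SAP*

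**What the plan says.** Willingness to use each product again is a secondary endpoint (Protocol 3.2, SAP 3.2). The secondary objective ties it to the 12-hour sessions.

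- **Timing on Days 1 to 4.** Protocol 5.1.3: "Document likelihood of subject using product again (Use the Product Again Questionnaire) after each 12-hour ad libitum use session". SAP 1.7 agrees: "After each 12-hour ad libitum use session, subjects will complete the Use the Product Again Questionnaire".
- **Day -1.** SAP 1.7 adds an administration before randomisation: "Subjects will be given a facilitated “Use the Product Again Questionnaire” after the product trials".
- **Early withdrawal.** Protocol 4.5: "Subjects withdrawn or dismissed by the investigator after enrollment (Day 1) will undergo End of Study procedures as feasible". Protocol 5.1.3.1 lists those procedures: a symptom-led examination, a review of medications and adverse events, and the cessation referral. There is no questionnaire.
- **Summary.** SAP 6.4: "Summary statistics [n (%)] will be computed for each level of the binary and 3-level endpoint, by test-product and by sequence". It names no denominator of its own.
- **Denominator.** The general rule in SAP 4.1 is "the denominator of percentages will be the number of subjects with nonmissing response data for the test product group". For categorical data collected at separate visits, "the denominator of the percentages of each category will be the number of subjects with a nonmissing value at the visit".
- **Missing data.** SAP 1.5 plans no imputation and allows dropouts to be replaced at the sponsor's discretion. The missing-at-random argument in SAP 4.2 concerns mixed models, and the questionnaire is not among the mixed-model responses in SAP 7.2.
- **Disposition.** SAP 5.0 tabulates discontinuations by sequence and adds a by-subject listing.

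**The concern.** A subject who leaves during a product's day because that product was not tolerated or not acceptable is likely to have been an unwilling respondent. Under the plan that subject has no Day 1 to 4 answer for the product and falls out of both numerator and denominator. The missingness is then related to the unseen answer, and its likely direction favours the product that caused the withdrawal. No model or imputation rule addresses it. The disposition table does not help directly, because each sequence contains all four products. At stake is the by-product willing percentage, which is descriptive.

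**Working it through.** **The plan's own figure.** SAP 1.5 gives 8 replications of 4 sequences: 4 × 8 = 32. This reproduces, and it is the full denominator for each product if nobody is lost. The documents give no dropout rate and no expected willing rate for this trial, so both are assumptions below.

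**Which denominator rule applies.** Both rules in SAP 4.1 count nonmissing answers only, so the result does not depend on the choice.

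**Formula.** Let w be the number willing and k the number who withdraw on a product's day because of it, before being asked, all of them in truth unwilling. The reported rate is w/(32 − k). The rate over all starters is w/32.

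| k | w = 20 (true 62.5%) | w = 24 (true 75.0%) |
|---|---|---|
| 0 | 20/32 = 62.5% | 24/32 = 75.0% |
| 1 | 20/31 = 64.5% | 24/31 = 77.4% |
| 2 | 20/30 = 66.7% | 24/30 = 80.0% |
| 3 | 20/29 = 69.0% | 24/29 = 82.8% |

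Each withdrawal adds 2.0 to 2.8 points. At k = 0 there is no bias.

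**If dropouts are replaced.** With k = 3 and 24 willing among 32 who answered, the report shows 24/32 = 75.0%, against 24/35 = 68.6% over all starters. The size is similar.

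**If some of those who left would have said willing.** Take 20 willing of 29 who answered and k = 3. If none of the three would have been willing, the overstatement is 69.0 − 62.5 = 6.5 points. If half would have been, it is 69.0 − (20 + 1.5)/32 = 69.0 − 67.2 = 1.8 points. It vanishes when their willing rate equals the reported rate.

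**How many to expect.** Protocol 1.2.2 gives two reference points:
- In an 8-hour ad libitum study of another product, 89 of 91 completed, with no reasons given for the other two: 2/91 × 32 = 0.7.
- In a pharmacokinetic study of other prototypes, 1 of 12 discontinued for adverse events: 1/12 × 32 = 2.7.

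Both figures assume that every loss falls on one product.

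**The case against.** Four stronger readings are tempting, and the documents do not support them.

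- **That the question is asked only after a full 12-hour session.** SAP 1.7 also gives it on Day -1. That answer follows a 10-minute trial before randomisation, so it cannot record a later reaction.
- **That anyone who stops using a product is lost.** The session permits use and sets no minimum: "the subjects will be allowed to use new cartridges with freshly charged" ad libitum. Someone who stops puffing but stays is still asked. Someone who leaves after answering is not lost for that product either.
- **That the willing rates are overstated as a matter of fact.** The bias is conditional. Subjects who are unwilling to use or cannot tolerate any product in the Day -1 trial do not continue, which makes later product-driven withdrawals less likely.
- **That 1 in 12 is the rate to expect.** It comes from smokers using a 5.0% nicotine prototype in a fixed hourly puffing regimen. This trial enrols e-vapor users, with products at 2.5% to 4.0%. The ad libitum study with 89 of 91 completers is closer in design.

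The size is also modest beside sampling error. At 20/32 a simple 95% interval is ±1.96 × √(0.625 × 0.375/32), about ±17 points, and no test or decision rests on the endpoint. Some cases may be traceable: sequence and stopping day identify the product, the primary reason for withdrawal is recorded (Protocol 4.5), and adverse events are listed by subject and product. A reduced n would also be visible.

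These points limit the concern but do not remove it. Listings do not correct a tabulated percentage, and sampling error does not excuse a bias with a likely direction. One further objection stands: coding a withdrawn subject as unwilling in the main table assigns an attitude that was never measured. A withdrawal also removes the subject from all later products, and the direction of that effect is unknown.

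**Conclusion.** The point holds in a narrow form. If a subject withdraws during a Day 1 to 4 product day because of that product, before the question is asked, the plan omits that subject from the product's willing percentage, which would then be biased upward. The size is about 2 to 3 points per withdrawal, assuming true willing rates of 62.5% to 75% of 32 and that those who withdraw would have answered unwilling. It is zero if there are no such withdrawals. The earlier studies suggest about 0.7 to 2.7 of 32 if all fell on one product, and the Day -1 trial should reduce that. This is a minor improvement to a descriptive secondary endpoint. It does not affect the primary analysis.

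**What to change.** 1. **Protocol 5.1.3.1:** add the Use the Product Again question, for the product in use, to the early-termination procedures, as feasible.
2. **SAP 6.4:** as an exception to SAP 4.1, report willing, unwilling and missing for each product over all subjects who started that product's Day 1 to 4 session, including any who were later replaced. Add a sensitivity line that counts as unwilling those who withdrew unanswered and whose recorded reason was that product.
3. **SAP 5.0:** show the product in use at discontinuation.

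The cost is one existing question at an existing contact, plus a few lines of SAP text. A few answers will follow a shorter exposure, and the willing percentages may come out slightly lower. If nobody withdraws and no answers are otherwise missing, the results are unchanged.

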4.2 METHODS FOR HANDLING DROPOUTS AND MISSING DATA

The primary and some secondary responses will be analyzed in a mixed effects ANOVA/ANCOVA framework wherein subjects and dependencies among multiple measures of the same endpoint, taken from the same subject (one in each of 4 periods), will be modeled as random effects. One advantage of such models is that the model estimates will be unbiased as long as any data that may be missing, are missing at random (MAR).^[7, 8] This method of dealing with missing data has been demonstrated by Food and Drug Administration statisticians and others to be superior to LOCF.^[9, 10]

Missing safety and demographic data will not be imputed.

Statistical Analysis Plan

4.3 SPECIFICATIONS FOR DISPLAYS

Displays will be produced by using the Courier New 8-point font. Headers will also be in Courier New 8-point font.

All displays are intended to be printed as landscape on 8.5×11 -in paper. The top and bottom margins will be 0.50 in, and the left and right margins will be 0.75 in.

Relative to the number of digits after the decimal in the original data, summary statistics will have the following number of digits after the decimal: mean, median, and percentiles - one more digit; standard deviation and standard error - two more digits; minimum, maximum, and range - same number of digits. Summary statistics will not exceed four digits after the decimal. Some laboratory parameters or other data may require deviation from this rule.

Percentages will be displayed with one digit after the decimal.

